| Study Title | Multipurpose Prevention of Post-Exposure Prophylaxis Regimens (Combo-PEP) |
| Study Design | 
To determine tissue pharmacology of a single dose of doxycycline for STI PEP, investigators at Emory University will collaborate with the Centers for Disease Control and Prevention (CDC) to conduct a clinical trial of up to 20 MSM and women aged 18-59, with measurement of anti-retroviral drug and doxycycline concentrations in the rectum and vaginal regions.
 
Study staff will plan to enroll participants who are HIV negative, at low risk for HIV and are not currently (or have no current plans) taking Post Exposure Prophylaxis (PEP) or Pre- Exposure Prophylaxis (PrEP). Enrolled participants will take a single dose of doxycycline (200mg) and Biktarvy® (200mg).
 
Biological specimens will be collected at 10 time points during this study. Study staff will recruit participants through existing research databases at the Hope Clinic and the Rollins School of Public Health, Research Match, and Clinical Data Warehouse. Internet and paper advertisements and community venues will also be used. At the first study visit, eligibility will be determined and screening blood work (approximately 14 mL), including an HIV test, will be performed. Participants will receive study drug in clinic and will provide documentation of taking doses (doxycycline and Biktarvy®) of the drug at home. During all study visits, participants will undergo blood collection (approximately 14 mL or 3 teaspoons of blood will be obtained), a urine sample, and collection of vaginal and rectal secretions. At certain visits, a vaginal and cervical biopsy will be performed on women, and a rectal biopsy will be performed on men, in addition to swab procedures. Women will have the option to do a rectal biopsy, as well. A pregnancy test will be done on women of childbearing potential at their screening and biopsy visit.
 |
| Primary Objective | To determine tissue pharmacology of single dose doxycycline for STI PEP |
| Secondary Objective(s) | To determine the tissue pharmacology of single dose bictegravir for HIV PEP. |

| | |
|---|---|
| Research Intervention(s)/Interactions | Doxycycline (200mg) and Biktarvy® (200mg) one combined dose |

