Doxycycline (DOX [200 mg]) is an oral medication used to treat or prevent infections that are strongly suspected to be caused by bacteria; it is an antimicrobial drug indicated for bacterial infections such as sexually transmitted infections.

Biktarvy

Biktarvy® (200mg) is an oral combination anti-HIV medication that contains the drugs tenofovir alafenamide, emtricitabine, and bictegravir.

Both study drugs will be stored and dispensed per manufacturer instructions by the Emory Investigational Drug Services Pharmacy Satellite location at the Hope Clinic. Prior to drug dispensing, the clinician will assess participant's medical history, and ensure the participant has no known allergies to the study drug. If a participant reports an allergy and a suitable alternative is not available, then the clinician may opt to not enroll the participant into the study.

6. Procedures Involved

When possible, study activities such as questionnaires will be done remotely due to the ongoing COVID-19 pandemic.

Phone Screening (if applicable): Potential participants may be identified from Hope Clinic databases of former study participants or self-referrals after seeing study flyers, social media ads, etc. In these cases, study staff will administer a pre-screening questionnaire via phone to assess preliminary eligibility. If the results of the pre-screening questionnaire indicate that the potential participant may be eligible for this study, they will be invited to the clinic to complete the first screening visit.

Screening Visit 1a: Potential participants will be asked about their medical history, undergo a physical exam, and have a peripheral blood sample drawn (17.2 mL) for lab tests (creatinine, complete blood count, coagulation, HIV and Hepatitis B) and research tests (baseline levels of study drug). A pregnancy test will also be performed on women of childbearing potential.

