Screening Visit 1b: Once all data (including screening labs) are collected, potential participants will be evaluated for eligibility. If found eligible, participants will have a blood sample drawn (2 mL), collect a self-administered rectal and/or vaginal fluid swab to test for gonorrhea and chlamydia, and provide a urine sample. If the participant tests positive for gonorrhea and/or chlamydia, the participant will be notified and referred for treatment to their primary doctor, health department, or other community STI treatment resources. Study staff will also dispense one dose of each study drug (200 mg of doxycycline and 200 mg of Biktarvy®) at this visit. Staff will provide dosing instructions to participant.

Dosing: Participants will be asked not to eat or drink anything except water after midnight the day before their scheduled dose. Participants will take both study drugs simultaneously at home approximately **1 hour before Visit 2** and will be instructed to take a timestamped photograph or videotape of themselves taking the dose. Photos and videos taken with smartphones automatically include a timestamp. Study staff will instruct participants to bring the photo/video to Visit 2 as proof of dosing. Participants will also have the option to send a text study staff at a specified number at the time of dosing if their phone does not have video/photo capabilities. Participants will be asked to abstain from receptive anal or vaginal sex from the time they take the study drug to 7 days after the biopsy procedure is completed in order to limit additional exposures (e.g. semen, douching, additional lubricants) to the rectal or vaginal mucosa.

Visit 2 (1 hour post-dose): Approximately 18 mL of blood will be drawn. Then participants will provide a urine sample and self- collect rectal or vaginal fluid swab samples.

Visit 3 (2 hours post-dose): Approximately 18 mL of blood will be drawn. Then participants will provide a urine sample and self- collect rectal or vaginal fluid swab samples.

Visit 4 (4 hours post-dose): Approximately 18 mL of blood will be drawn. Then participants will provide a urine sample and self- collect rectal or vaginal fluid swab samples.

Visit 5 (8 hours post-dose): Approximately 18 mL of blood will be drawn. Then participants will provide a urine sample and self- collect rectal or vaginal fluid swab samples.

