Visit 6 (24 hours post-dose): Approximately 18 mL of blood will be drawn. If the participant has a penis, one urethral swab and one glans swab will be collected. If the participant has a vagina, a vaginal swab will be collected. A urine sample will then be collected from all participants.

Participants who have a vagina will undergo a vaginal/cervical biopsy. All other participants will undergo a rectal biopsy. Participants who complete the vaginal biopsy will have the **option** to also undergo the rectal biopsy at Visit 6. Once the scope (rectal) or the speculum (vaginal) is inserted, additional swabs will be inserted in the rectum or vagina to collect secretions. Then, up to 12 rectal biopsies, or 1 to 2 vaginal and 1 to 2 cervical biopsies will be collected. All participants will be informed not to place anything into the rectum or vagina and abstain from intercourse for 7 days after their biopsy procedure(s) to allow the mucosa to heal.

Vaginal and cervical tissue samples will not be collected in women who are menstruating, pregnant, or have possible cervical or vaginal infection. A pregnancy test will be administered to women of childbearing potential to ensure they are not pregnant. Visit 2 will also be scheduled 7 to 10 days after their last menstrual cycle.

Visit 7 (48 hours post-dose): Approximately 18 mL of blood will be drawn. Then participants will provide a urine sample and self- collect rectal or vaginal fluid swab samples.

Visit 8 (72 hours post-dose): Approximately 18 mL of blood will be drawn. Then participants will provide a urine sample and self- collect rectal or vaginal fluid swab samples.

Visit 9 (96 hours post-dose): Approximately 18 mL of blood will be drawn. Then participants will provide a urine sample and self- collect rectal or vaginal fluid swab samples.

Visit 10 (7 days post-dose): Approximately 18 mL of blood will be drawn. Then participants will provide a urine sample and self- collect rectal or vaginal fluid swab samples.

Timing of procedures after dose: The procedures conducted after dose, particularly those less than 24 hours after dose, should occur as close to the scheduled time points as possible. Protocol deviations will be not filed for visits that occur outside of the target windows but will be noted in source documents.

Contingency visit: If needed, participants may be brought in for additional study visits. This would occur if, for example, screening laboratory results are lost or are inconclusive.

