To protect against possible side effects of the study drug, women who are pregnant or nursing a child may not take part in this study. If a female participant becomes pregnant, there may be risks to the participant, the embryo, or fetus. These risks are not yet known. Women of childbearing potential will be asked to provide a urine pregnancy test to ensure they are not pregnant, prior to administering drug. Women of childbearing ability will discuss contraceptive methods to use throughout the study and may be asked to abstain throughout the duration of the study. If the participant becomes pregnant during the study, they must inform the study doctor immediately. Pregnant women will be excluded or removed from the study.

Biktarvy® (TAF/FTC/BIC)

Biktarvy® is a combination anti-HIV medication that contains the drugs tenofovir alafenamide, emtricitabine, and bictegravir. Based on clinical trials previously conducted of Biktarvy®, the drug showed to be well tolerated (see package insert). The most common adverse events reported in clinical trials ($\geq 5\%$ incidence) included diarrhea, nausea, and headache. Additional adverse reactions occurring in less than 2% of subjects administered Biktarvy® included vomiting, flatulence, dyspepsia, abdominal pain, rash, and depression.

Renal toxicity and bone density loss are rarely reported with chronic use of TAF containing products and are not expected to occur with the dose regimen prescribed in this protocol. Similarly, lactic acidosis and severe hepatomegaly have rarely been associated with medications in the same class as TAF and FTC; however, are not expected to occur with this regimen.

Use of TAF/FTC can also cause flare-ups in those who have hepatitis B virus. It can cause the Hepatitis B virus to suddenly return in a worse form than before if treatment was provided (see package insert). For this reason, it is important that participants not participate in the study if they are known to have Hepatitis B. Nonetheless, the maximum 1-day dosing regimen for this study is unlikely to cause flare-ups in Hepatitis B even if not diagnosed.

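### The only scheduled pre-dose pregnancy test is at Visit 1a, up to 42 days before the dose; adding one at Visit 1b, where drug is dispensed, is a cheap safety improvement with very low expected yield

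*Combined protocol and SAP*

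**What the plan says.** **The commitment.** Section 15 (Doxycycline): "Women of childbearing potential will be asked to provide a urine pregnancy test to ensure they are not pregnant, prior to administering drug". No visit or time limit is given.

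**Where tests are scheduled.** The synopsis: "A pregnancy test will be done on women of childbearing potential at their screening and biopsy visit". Section 6, Screening Visit 1a: "A pregnancy test will also be performed on women of childbearing potential". Section 6, Visit 6 (24 hours post-dose): "A pregnancy test will be administered to women of childbearing potential to ensure they are not pregnant". Table 1 marks a test at Visit 1a and leaves Visit 1b and the dose column blank. As extracted, its second mark falls under Visit 7 instead of Visit 6. That may be a column shift in the PDF reading, and both visits follow the dose.

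**What happens at Visit 1b.** Eligibility is judged there, and participants have blood drawn, self-collect a "fluid swab to test for gonorrhea and chlamydia, and provide a urine sample". Drug is handed over at the same visit: "Study staff will also dispense one dose of each study drug". No pregnancy test is listed.

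**The dose.** "Participants will take both study drugs simultaneously at home approximately" one hour before Visit 2. No clinic visit is scheduled between Visit 1b and the dose.

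**Timing.** Table 1 gives Visits 1a and 1b the same window, -42 to 0 days. In the Visit 6 text on biopsies, for women: "Visit 2 will also be scheduled 7 to 10 days after their last menstrual cycle".

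**The concern.** The stated purpose of the test is to make sure that a woman is not pregnant when she receives the drugs. The schedule can be followed to the letter with a result that is six weeks old. The visit at which staff last see her before exposure, and at which they hand her the drugs, has no test listed. A pregnancy that was not detectable at Visit 1a could then first come to light at the biopsy visit. A positive result there can stop the biopsy but cannot undo the exposure.

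The stake is participant safety. Section 15 bars pregnant women and says that the risks to the embryo or fetus are unknown. Section 16 expects no direct benefit to participants. Section 19 counts spontaneous and elective abortions as serious adverse events, although that is a reporting definition and not evidence of harm from a single dose.

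**Working it through.** The plan states no figure to reproduce here. The check is a reading of the schedule, followed by a conditional illustration of size.

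**1. Schedule.** Pregnancy tests before the dose: one, at Visit 1a. Tests listed at Visit 1b: none. Permitted gap from the Visit 1a test to the dose: 0 to 42 days (Table 1). Women to be enrolled: 10 (Section 12). Fewer may be of childbearing potential, because the synopsis includes trans women in this group.

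**2. Assumptions, none from the documents.** A urine test turns positive *d* = 7 to 14 days after conception. Conception occurs at 1% to 3% per 28 days, spread evenly over time. The illustrative test is done 7 days before the dose.

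**3. If the menses rule works.** The dose falls at most 10 days after menstruation, so any conception is at most 10 days old at dosing.
- Test 7 days before the dose: the oldest conception is 10 - 7 = 3 days old, below the shortest assumed lag of 7 days. It finds none.
- Test on the dosing day: at *d* = 7 it finds (10 - 7)/10 = 30% of these conceptions. At *d* of 10 days or more it finds none.

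A long gap after Visit 1a also matters little here, because a later dosing slot opens only after another bleed.

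**4. If the menses rule fails.** Let *g* be the gap from the Visit 1a test to the dose. Conceptions that go undetected before dosing fall in a span of *g* + *d* days under the present schedule, and 7 + *d* days with the added test. The difference is *g* - 7 days, whatever *d* is.

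| Gap *g* (days) | Days closed, *g* - 7 | Exposed pregnancies avoided per 100 such women, at 1% to 3% per 28 days |
|---|---|---|
| 42 | 35 | 35/28 × (1 to 3) = 1.25 to 3.75 |
| 28 | 21 | 21/28 × (1 to 3) = 0.75 to 2.25 |
| 14 | 7 | 7/28 × (1 to 3) = 0.25 to 0.75 |
| 7 or less | 0 | 0 |

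At *g* = 42 the undetected span falls from 49 to 14 days if *d* = 7, and from 56 to 21 days if *d* = 14.

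**5. Trial level.** The documents do not say how many women would fall outside the rule. If one did, at the 42-day gap, the expected number avoided is 0.0125 to 0.0375, or about 0.01 to 0.04.

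**The case against.** The strongest objection is that nothing is breached. A test at Visit 1a comes before the drug, and Section 15 names no visit, so a test at Visit 1b is also allowed. The synopsis speaks of screening, and Visit 1b is labelled a screening visit. This stands as far as it goes: a reader might infer that Section 15 contradicts the schedule, and it does not. What remains is that neither the Visit 1b text nor Table 1 lists a test there, so the plan as written does not cause one to be done.

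The second objection is that the added test does nothing when the menses rule is followed. For a test 7 days before the dose this is right, and step 3 shows it. A reader might also infer that irregular cycles defeat the rule. They do not, since the slot still opens only after a bleed, however late. The rule fails when bleeding is misreported or is not menstrual.

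Other safeguards exist. Section 10 asks for willingness to use condoms and no plans for pregnancy. Section 15 calls for a discussion of contraception and possibly abstinence. Section 5 has a clinician review medical history before dispensing, and Section 14 removes a participant who newly meets an exclusion criterion. These lower the risk, but none is a test. The firm request to abstain from receptive sex starts only at the dose.

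The assumed conception rates may be too high for these women: over 13 periods of 28 days they compound to 1 - 0.99^13 = 12% and 1 - 0.97^13 = 33% a year. The yield could therefore be smaller still. Table 1 as extracted is also weak support, because it omits the Visit 1b urine that Section 6 collects. The absence of a test at Visit 1b rests mainly on the Section 6 text and the synopsis.

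One point favours acting. The plan repeats the test at the biopsy visit although the same menses rule governs that cycle, so it does not itself treat the rule and the Visit 1a test as enough before a biopsy.

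**Conclusion.** The point holds as a low-severity safety improvement. The written schedule permits dosing on a pregnancy test up to 42 days old and lists none at the last scheduled clinic visit before the dose. The 42 days is a ceiling, and nothing in the documents says that it is typical. The benefit is confined mainly to women in whom the menses rule fails: 1.25 to 3.75 exposures avoided per 100 such women at the longest gap, and none at a gap of 7 days or less. These figures rest on assumed conception rates and an even spread of conceptions. The number of such women among the 10 is unknown, so the trial-level yield cannot be stated beyond being very small.

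A reader might infer that pregnant women are likely to be dosed, or that the pharmacokinetic results are at risk. The documents support neither, and no effect on the results is claimed.

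**What to change.** For women of childbearing potential, run a urine pregnancy test at Visit 1b on the urine that Section 6 already collects there, and require a negative result before dispensing. List the test in the Visit 1b text, name that visit in the Section 15 sentence, mark it in Table 1, and keep the biopsy-visit test.

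Schedule Visit 1b close to the planned dose. State a short maximum interval from test to dose, for example 7 days. If dosing slips past it, require a repeat negative test before the dose. A dipstick dispensed at Visit 1b for home use, with the result reported to staff before dosing, would avoid an extra clinic visit.

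**Cost.** About 10 dipsticks at most at Visit 1b, a take-home spare where the home route is used, and wording changes in Sections 6 and 15 and Table 1. If Table 1 is right that no urine is taken at Visit 1b, one extra urine sample per woman is needed. Scheduling of Visit 1b becomes slightly tighter, because drug can no longer be dispensed far ahead of the dose. A dipstick can miss a conception of the last few days, so it backs up the menses rule and does not replace it.

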Acquisition of HIV drug resistance is a theoretic concern for HIV positive people taking intermittent dosing of anti-HIV medication. For this protocol, study staff will test participants for HIV at study entry and monitor clinically for high-risk behavior or any signs of acute HIV infection at study visits. If high-risk behavior (e.g. unprotected anal intercourse with a man of unknown HIV status) or symptoms of acute HIV infection are reported, and HIV antibody test will be repeated, and the participant will be counseled about the need for any follow-up testing. Clinical signs and symptoms of acute HIV infection that will be queried include: fever, fatigue, malaise, skin rash, swollen glands, oral/genital ulcers, myalgia/arthralgia. [name] will review all reports of clinical signs/symptoms to determine appropriate follow-up and linkage to care as necessary. If a diagnosis of acute HIV infection is thought to be possible or determined by

repeat HIV testing, the participant will be discontinued from the study. For this protocol, study staff will test participants for HIV at study entry and monitor clinically for high-risk behavior or any signs of acute HIV infection at study visits.

Participants will be asked to abstain from receptive anal or vaginal sex from the time they take the study drug to 7 days after the biopsy procedure is completed in order to limit additional exposures (e.g. semen, douching, additional lubricants) to the rectal or vaginal mucosa.

Participants taking Biktarvy® will be counseled that they should not expect to achieve protection from HIV infection by taking drug during this study, as they will be provided a limited supply. All participants included in the study that have an interest in taking PrEP for HIV prevention, will be referred to an area PrEP provider at the termination of the study. The Hope Clinic has compiled a resource sheet of area providers that will be distributed to interested participants.

Blood Sample Risks

The most common risks of blood sample collection are pain at the puncture site, bruising, and a feeling of lightheadedness. To minimize these risks, blood draws will be performed by trained personnel, and will be performed in a secure environment with access to first aid equipment, bandages, and trained healthcare professionals.

16. Potential Benefits to Participants

Subjects are not expected to derive direct benefit from this study.

17. Compensation to Participants

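### A participant with nothing to report is not retested for HIV between Visit 1a (up to 42 days before) and the at-home Biktarvy dose: a small safety gap with a cheap fix

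*Combined protocol and SAP*

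**What the plan says.** The synopsis (Study Design) puts the HIV test at the first study visit: "screening blood work (approximately 14 mL), including an HIV test, will be performed". Section 6 agrees and lists it at Visit 1a among the "lab tests (creatinine, complete blood count, coagulation, HIV and Hepatitis B". Table 1 lets Visits 1a and 1b each fall anywhere from 42 days before the dose up to the dose, and it has no HIV-test row for any visit.

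At Visit 1b (Section 6) eligibility is settled, 2 mL of blood is drawn for an unstated purpose, and swabs and urine are collected. The swabs are for gonorrhea and chlamydia. The drug is handed over at the same visit ("Study staff will also dispense one dose of each study drug"). Later, "Participants will take both study drugs simultaneously at home", about an hour before Visit 2. For women, "Visit 2 will also be scheduled 7 to 10 days after their last menstrual cycle".

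Section 15 (Biktarvy) sets out the HIV safeguards: "study staff will test participants for HIV at study entry and monitor clinically for high-risk behavior". Staff also ask about named symptoms of acute infection at study visits. Reported symptoms or high-risk behavior lead to a repeat antibody test and counseling on follow-up testing. Symptom reports are reviewed, and a participant is discontinued if acute infection is considered possible, even without a positive test. The section treats resistance as a theoretical concern in HIV-positive people who dose intermittently.

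On background risk, the synopsis says "Study staff will plan to enroll participants who are HIV negative, at low risk for HIV", while its Study Population row speaks of people at risk of infection.

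**The concern.** The safeguards that follow the Visit 1a test depend on the participant having something to report. Someone infected around or after Visit 1a who has no symptoms, or does not disclose a risk, is not retested and takes a three-drug antiretroviral as HIV negative. The requested abstinence starts with the dose, so it does not cover the screening interval. A positive gonorrhea or chlamydia result at Visit 1b leads to notification and referral, but is not named as a trigger for HIV testing.

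The protocol names two consequences of unrecognized infection: resistance (Section 15, Biktarvy) and possibly greater transmission to partners after biopsy bleeding (Section 15, Rectal Biopsies). One-week abstinence counseling already limits the second.

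The assay wording is a secondary matter. The stated target of the triggered repeat is acute infection, yet the only test named is an antibody test. That such a test can miss early infection is a general assumption here, because the documents give no window period.

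**Working it through.** **Is there a scheduled test between Visit 1a and the dose?** The documents do not define study entry. If it means Visit 1a, the test may be 42 days old at dosing. If it means enrollment, Section 19 (Adverse Events) places that at Visit 2, about 1 hour after the dose, and Visit 2 lists no HIV test. If it means Visit 1b, where eligibility is decided, no HIV test is written there, although the 2 mL draw is unexplained. No reading gives a written test between Visit 1a and the dose.

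**Is the 42-day maximum usable?** From Visit 1a to Visit 10 is 42 + 7 = 49 days, within the 8-week (56-day) limit in Section 9. It is usable.

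**Size.** The plan gives no figure to reproduce. Inputs from the documents are 20 participants (Section 12) and a gap of at most 42 days (Table 1). The assumed input is HIV incidence *i* of 0.1 to 5 per 100 person-years.

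Expected infections in a gap of *g* days = 20 × (1 − exp(−*i* × *g* / 365.25)), with *i* per person-year. At *i* = 0.01 and *g* = 42 this is 20 × 0.001149 = 0.0230.

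| Incidence per 100 person-years | 42-day gap | 14-day gap | 7-day gap |
|---|---|---|---|
| 0.1 | 0.0023 | 0.0008 | 0.0004 |
| 0.5 | 0.0115 | 0.0038 | 0.0019 |
| 1 | 0.0230 | 0.0077 | 0.0038 |
| 5 | 0.1147 | 0.0383 | 0.0192 |

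Over 42 days, the chance that at least one of the 20 is infected is 0.2%, 2.3% and 10.9% at 0.1, 1 and 5 per 100 person-years. These figures are before any safeguard acts.

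**What a timed retest removes.** Subtract the columns, taking the 42-day gap as the starting point:

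- Visit 1b at 7 days: 0.0023 − 0.0004 = 0.0019 at the lowest incidence, and 0.1147 − 0.0192 = 0.0955 at the highest.
- Visit 1b at 14 days: 0.0023 − 0.0008 = 0.0015, and 0.1147 − 0.0383 = 0.0764.
- If questioning at Visit 1b already intercepts half (an assumption), the 7-day figures halve to about 0.001 and 0.048.
- If Visit 1b is no nearer the dose than Visit 1a, the retest removes nothing.

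**Relative reduction, as illustration only.** For a retest 7 days before the dose and an assay window of *w* days, the reduction from a 42-day gap is 1 − (7 + *w*)/(42 + *w*). It is 83%, 67%, 49% and 40% for assumed windows of 0, 10, 30 and 45 days. These figures depend wholly on the assumed timing and window.

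**Why the assay should be named.** The chance of at least one undetected infection at the dose is 1 − exp(−20 × *i* × (*g* + *w*)/365.25). At *i* = 0.01:

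- No retest, 42-day gap, assumed 45-day antibody window: 20 × 0.01 × 87/365.25 = 0.0476, giving 4.7%.
- Retest on the day of dosing with the same antibody assay (*g* = 0): 2.4%.
- Retest on the day of dosing with an assumed 10- to 18-day antigen or RNA window: 0.5% to 1.0%.

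**The case against.** The strongest reply is that no harm is shown. The trial gives a single dose, whereas the resistance remark concerns intermittent dosing and calls the risk theoretical. Recruitment aims at low risk, condom use is an inclusion criterion, and suspicion alone is enough to discontinue. At 0.5 per 100 person-years, a 21-day gap and half of infections intercepted by questioning, a retest at 7 days keeps (0.0057 − 0.0019)/2 = 0.0019 infected participants from dosing, or about one per 500 repeats of this trial. All of this stands and sets the low priority.

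A second reply is that a retest at Visit 1b may achieve nothing, because Visit 1b shares the 42-day window and a test with a long blind period adds less. This also stands. It is why the change needs a time limit and a named assay.

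A third reply is that a test at Visit 1b may already be intended: the 2 mL draw has no stated purpose, and Table 1 has no HIV row even for Visit 1a. That cannot be excluded. If a test is intended, writing it down is most of the remedy.

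A reader might infer that HIV is ignored after screening. The documents do not support that, since Section 15 has active questioning, triggered testing, review of symptom reports and discontinuation on suspicion. A reader might also infer that participants face a material risk of resistance. The documents give no such probability, and none can be derived from them.

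**Conclusion.** The point holds as a minor safety improvement. No HIV test is written between Visit 1a and the antiretroviral dose for a participant with nothing to report, and that interval may reach 42 days. The expected number of infections in it is about 0.002 to 0.11 among 20 participants before safeguards. This rests on an assumed incidence of 0.1 to 5 per 100 person-years and on everyone having the maximum gap. Actual gaps are unknown. Low-risk recruitment and condom use favor the lower end, although the two synopsis descriptions of risk do not fully agree.

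The antibody wording is secondary. Because discontinuation needs no positive result and follow-up testing is discussed, a better assay mainly serves correct diagnosis and linkage to care. Nothing here touches the concentration endpoints, the sample size or the Wilcoxon comparisons.

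**What to change.** 1. Section 6 (Visit 1b) and Table 1: run an HIV antigen/antibody or RNA test on the Visit 1b blood. Hold Visit 1b within a stated limit before the dose, for example 7 days, or 14 days where menstrual-cycle scheduling requires it. Confirm a negative result before dosing. The drug can still be dispensed at Visit 1b, with the result relayed through the existing calls or texts. The time limit is essential.
2. Section 15 (Biktarvy): replace the reference to study entry with Visits 1a and 1b.
3. Section 15 (Biktarvy): name the triggered repeat as an antigen/antibody or RNA test.

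The cost is about 20 extra assays, perhaps slightly more than 2 mL of blood at Visit 1b, and a more sensitive assay for the few triggered repeats. Scheduling becomes somewhat tighter, chiefly for women. A false positive would occasionally delay a participant until it is resolved. No extra visit, staff or invasive procedure is needed.
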